#### 7.5. Rescue Medications and Supportive Care

Patients should receive appropriate supportive care measures as deemed necessary by the treating investigator.

#### 7.6. Treatment of Overdose

No specific information is available on the treatment of overdose of IFX-1. For this study, an overdose of IFX-1 will be defined as any single dose of > 1,200 mg. In the event of overdose, the participant should be observed closely for signs of toxicity. Appropriate supportive treatment should be provided if clinically indicated.

In the event of an overdose, the investigator should:

1. Contact the medical monitor immediately
2. Closely monitor the patient for any AE/SAE and laboratory abnormalities

3. Obtain a plasma sample for PK analysis as close as possible to the administration of overdose if requested by the medical monitor (determined on a case-by-case basis).
4. Document the quantity of the excess dose as well as the duration of the overdose in the eCRF

Decisions regarding dose interruptions or modifications will be made by the investigator in consultation with the medical monitor based on the clinical evaluation of the patient.

## **8. STUDY ASSESSMENTS AND PROCEDURES**

### **8.1. Phase II**

Study procedures and their timing for Phase II are summarized in the Schedule of Assessments (SoA; Table 1).

Details on the assessments and procedures are given in the following subsections.

Safety concerns should have been discussed with the sponsor immediately upon occurrence or awareness to determine if the patient should continue or discontinue any IMP.

Adherence to the study design requirements, including those specified in the SoA (Table 1), was essential and required for study conduct.

All screening evaluations must have been completed and reviewed to confirm that potential patients met all eligibility criteria (Section 6.1). The investigator was to maintain a screening log to record details of all patients screened and to confirm eligibility or record reasons for screening failure, as applicable.

#### **8.1.1. Baseline Assessments**

The following procedures were to be performed to assess baseline characteristics during screening evaluations and before IMP administration:

- Documentation of demographic details (age, gender, race, and ethnicity), medical and disease history (see Sections 8.1.1.1 and 8.1.1.2)
- Disease assessments (see Section 8.1.2)
- Documentation of concomitant disease and concomitant medications (see Sections 8.1.1.3 and 8.1.1.4)
- Baseline safety assessment (height, weight, physical exam, vital signs, AEs, and safety laboratory; see Section 8.1.3)

#### **8.1.1.1. Medical History (Except COVID-19 history)**

The documentation of the patient's medical history were to include any details on the patient's medical history before enrollment into the study. The information must have been documented as such in the source documentation and eCRF.

#### **8.1.1.2. COVID-19 History**

Any details on the patient's COVID-19 disease history including any COVID-19 therapy (onset of symptoms, medications, oxygen support, intubation, SARS-CoV-2 testing) by verbatim name with start and end dates, dosages, modality) that the patient received were to be documented in the source documentation and in the eCRF.

#### **8.1.1.3. Concomitant Disease**

All diseases that the patient was experiencing at enrollment into the study or after enrollment until EOT were to be regarded as concomitant diseases. All concomitant diseases must have been documented in the source documentation and in the eCRF.

#### **8.1.1.4. Prior and Concomitant Medications**

All drugs being taken by a patient at enrollment into the study or after enrollment until EOT were to be regarded as concomitant medication.

All prior medications taken by the patient within 2 weeks before enrollment into the study and all concomitant medications must have been documented in the source documentation and in the eCRF. Details on prior and concomitant medications must have included the reason for use, administration start and stop dates, and dosing information, including dose, route, and frequency of administration.

### **8.1.2. Efficacy Assessments**

#### **8.1.2.1. Imaging Requirements**

CT scan, MRI, or X-ray for COVID-19 assessment were to be performed locally at each scheduled disease assessment time point, and at any time when disease progression was suspected.

The choice of whether the imaging was by CT scan, MRI, or X-ray was an investigator decision. Once the imaging choice had been made, subsequent assessments should have been made using the same modality whenever possible.

#### **8.1.2.2. Evaluation of Lung Function**

- Oxygenation index (PaO2 / FiO2)
- Respiratory rate
- Oxygen supplementation: room air, flow O2 (L/min) if extubated

- Ventilation status (invasive/non-invasive/intermittent non-invasive)
- Mode of ventilation (e.g., CPAP/BIPAP)
- Other oxygenation support
  - Type of oxygen mask or nasal canula, or other mechanical ventilation mode and parameters, as applicable, should have been documented
- Intubation and extubation dates, as well as date of tracheostomy should have been documented

#### **8.1.2.3. Evaluation of Response**

- SARS-CoV-2 mRNA testing was to be performed in context of enrolment procedures and at one to four additional time points at discretion of the investigator

##### **8.1.2.3.1. Evaluation of Early Response**

**Early Response** as defined as meeting **ALL** of the following criteria at day 7 after enrollment:

- Patient alive and extubated OR oxygenation index  $\geq 300$  OR improvement of  $\geq 30\%$  from baseline,
- Temperature  $< 38^{\circ}\text{C}$  in absence of fever decreasing medication of at least 4h
- White blood cell count within normal limit of local lab quantifications

##### **8.1.2.3.2. Evaluation of Late Response**

**Late Response** as defined by either being **discharged alive** from hospital until day 28 **OR** meeting **ALL** of the following criteria at day 28 of the trial:

- Patient alive and extubated
- Patient discharged from ICU
- Patient free of shortness of breath (respiratory rate  $< 20$ ) in absence of oxygen supply
- Patient free of fever ( $< 37.6^{\circ}\text{C}$ )

#### **8.1.3. Safety Assessments**

Safety was to be assessed based on the following variables:

- AEs (see Section 8.1.3.1)
- Laboratory safety parameters (see Section 8.1.3.2)
- Vital signs (see Section 8.1.3.3)
- Electrocardiograms (see Section 8.1.3.4)
- Physical examination (see Section 8.1.3.5)

Planned time points for all safety assessments are provided in the SoA (Table 1).

#### **8.1.3.1. Adverse Events Assessments**

Adverse events were to be assessed throughout the study from the time of enrollment to the EOT visit as specified in the SoA (Table 1). For details on AE collection and reporting, see Section 9.1. The investigator should have taken appropriate measures to follow all AEs until clinical recovery was complete and laboratory results had returned to normal, or until progression had been stabilized, or until death, in order to ensure the safety of the patients. This may imply that observations would continue beyond the last planned visit per protocol, and that additional investigations may have been requested by the sponsor. When study treatment was prematurely discontinued, the patient's observation was to be continued until the EOT visit for that patient as defined by the protocol.

#### **8.1.3.2. Clinical Safety Laboratory Assessments**

In general, blood samples for safety laboratory analysis should have been obtained once a day during a routine sampling (preferable in the morning) before administration of IMP. Additional tests may have been performed at any time during the study as determined necessary by the investigator or required by local regulations.

See Appendix 1, Table 3 for the list of clinical laboratory tests performed and the SoA (Table 1) for timing and frequency.

The investigator must have reviewed the laboratory report, documented this review, and recorded any clinically relevant changes (clinically relevant abnormal findings) occurring during the study in the AE section of the eCRF. The laboratory reports must have been filed with the source documents. Clinically relevant abnormal laboratory findings were those which were not associated with the underlying disease, unless judged by the investigator to be more severe than expected for the patient's condition.

All laboratory tests with values considered clinically relevantly abnormal and with onset before EOT visit should have been reported in the AE section of the eCRF and repeated until the values returned to normal or baseline, were no longer considered clinically relevant by the investigator or medical monitor, or until the EOS visit (also see Section 8.1.4 and Appendix 3).

If such values did not return to normal/baseline within a period of time judged reasonable by the investigator, the etiology should have been identified, and the sponsor notified.

All protocol-required laboratory assessments, as defined in Appendix 1, Table 3, must have been conducted in accordance with the SoA (Table 1).

If laboratory values from non-protocol specified laboratory assessments performed at the institution's local laboratory required a change in patient management or were considered

clinically relevant by the investigator (e.g., SAE or AE or dose modification), then the results must have been recorded in the eCRF.

Blood samples for serum pregnancy testing were to be collected on the same day as safety laboratory testing. For details on pregnancy testing, refer to Appendix 4.

#### **8.1.3.3. Vital Signs**

Core body temperature, heart rate, respiratory rate, and blood pressure (diastolic and systolic) were to be assessed at each visit at pre-dose on the days of IMP administration and at further time points whenever medically indicated.

Blood pressure and pulse measurements were to be assessed with a completely automated device. Manual techniques were to be used only if an automated device was not available.

Vital signs were to be measured in a supine position (after a rest of at least 1h in case of position switch from prone position), preferably in the morning. Three readings of blood pressure and pulse were to be taken. The first reading should have been rejected. The second and third readings should have been averaged to give the measurement recorded in the eCRF.

#### **8.1.3.4. Electrocardiograms**

12-lead electrocardiogram (ECG) was to be obtained as outlined in the SoA (Table 1) using an ECG machine that automatically calculated the heart rate and measured PR, QRS, QT, and QTc intervals.

#### **8.1.3.5. Physical Examination**

A physical examination was to be conducted at screening and each study visit.

The physical examination included, at a minimum, assessments of the skin, cardiovascular, respiratory, gastrointestinal, and neurological systems. Height (at screening) and weight was also to be measured and recorded as specified in the SoA (Table 1).

Investigators should have paid special attention to clinical signs related to previous serious illnesses.

#### **8.1.3.6. Survival Status**

The patient survival status were to be assessed during the study and follow-up and documented in the eCRF. In case the patient died and the date of death was unknown, the date of the last personal contact should have been documented at a minimum.

#### **8.1.4. Pharmacokinetics/Pharmacodynamics**

If possible, blood samples were to be collected pre-dose for measurement of plasma concentrations and C3a and C5a of IFX-1 as specified in the SoA (Table 1). IFX-1 concentrations were to be measured for all patients in citrate plasma and analyzed by a specialized laboratory using Enzyme-Linked ImmunoSorbent Assay.

Detailed instructions regarding the collection, processing, etc., of samples were to follow local regulations and requirements.

#### **8.1.5. Biobanking of Samples from Patients Treated at Amsterdam Medical Center**

COVID-19 is a new viral disease with distinct clinical and pathophysiological features, which differentiate COVID-19 from other viral diseases such as Influenza. A COVID-19 dedicated Biobank was established at the Amsterdam Medical Center (AMC) in order to investigate further COVID-19 pathophysiological characteristics. Therefore, it was planned to store all remaining AMC study patient derived biomaterials, including but not limited to blood, bronchial lavage fluid, and tissue in the AMC COVID-19 Biobank. Patients were to be asked for a separate informed consent.

### **8.2. Phase III**

Study procedures and their timing for Phase III are summarized in the SoA (Table 2).

Details on the assessments and procedures are given in the following subsections.

Safety concerns should be discussed with the sponsor immediately upon occurrence or awareness to determine if the patient should continue or discontinue any IMP.

Adherence to the study design requirements, including those specified in the SoA (Table 2), is essential and required for study conduct.

All screening evaluations must be completed and reviewed to confirm that potential patients meet all eligibility criteria (Section 6.2). The investigator will maintain a screening log to record details of all patients screened and to confirm eligibility or record reasons for screening failure, as applicable.

#### **8.2.1. Baseline Assessments (Screening)**

The following procedures will be performed to assess baseline characteristics during screening evaluations and before randomization and IMP administration:

- Check inclusion and exclusion criteria

- Documentation of demographic details (age, gender, race, and ethnicity), medical and COVID-19 history (see Sections 8.2.1.1 and 8.2.1.2). Race information is required for eGFR calculation using the CKD-EPI equation
- 8-point ordinal scale assessment (see Section 8.2.2.2) and oxygenation index ( $\text{PaO}_2 / \text{FiO}_2$ ; one representative measurement within 6h before randomization)
- Documentation of concomitant disease and prior medications (see Sections 8.2.1.3 and 8.2.1.4)
- Baseline safety assessment (height, weight, physical exam, AEs, ECG, urine analysis, pregnancy test, and clinical safety laboratory [including creatinine assessment]); see Section 8.2.3)

#### **8.2.1.1. Medical History (Except COVID-19 History)**

The documentation of the patient's medical history includes any details on the patient's medical history before randomization into the study. The information must be documented as such in the source documentation and eCRF.

#### **8.2.1.2. COVID-19 History**

Any details on the patient's COVID-19 disease history including any COVID-19 therapy (onset of symptoms, medications, oxygen support, intubation and tracheostomy dates, SARS-CoV-2 polymerase chain reaction (PCR) test date and result by verbatim name with start and end dates) that the patient received will be documented in the source documentation and in the eCRF.

#### **8.2.1.3. Concomitant Disease**

All diseases that the patient is experiencing at screening/randomization until end of treatment are regarded as concomitant diseases. All concomitant diseases must be documented in the source documentation and in the eCRF.

#### **8.2.1.4. Prior and Concomitant Medications and Procedures**

All procedures performed or medications administered within 7 days before randomization should be recorded as prior procedures and prior medication with generic name, start date, stop date, and indication for treatment.

Reporting of prior and concomitant medications will follow special considerations for conditions in the ICU. A complete record of all prior and concomitant medications (but excluding nutritional and volume therapy, electrolyte support, vitamins, non-steroidal anti-inflammatory drugs (NSAIDs), and supportive therapies such as artificial tears, ointments, stool softeners/laxatives, etc.) will be maintained in the eCRF for each participant, beginning 7 days before randomization and continuing up to 30 days after the last dose of study treatment).

In addition, a complete record of all steroid and antibiotic therapy, as well as any therapy (medications, specific treatments, etc.) associated with or used in the assessment or treatment of an AE will be documented for the duration of the study.

The following information must be recorded in the eCRF for each reportable concomitant medication: generic name, route of administration, start date, stop date, and indication (Appendix 12).

### **8.2.2. Endpoint Assessments**

#### **8.2.2.1. Evaluation of Organ Support**

- Renal replacement therapy, extracorporeal membrane oxygenation (ECMO), mechanical ventilation
- Extubation and re-intubation dates should be documented

#### **8.2.2.2. Ordinal Scale Evaluation**

8-point ordinal scale score will be documented at the visits specified in the SoA (Table 2), including the date (one value per assessment day, that best represents the patient's condition at that day).

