## CONFIDENTIAL

Screening/ Randomization	Treatment Period IMP administration and assessments as long as in ICU / Hospital									Follow-up Period (Telephone possible)	
	Week 1			Week 2	Week 3	Week 4	Week 5	Any time		FUV	
	Screening not more than 24h before randomization	Day 1 (at-or up to 24h after random- ization)	Day 2	Day 4	Day 8	Day 15	Day 22	Day 28 (if still in hospital)	ICU discharge	Hospital discharge	Day 28
Endpoint Assessments											
Organ support (renal replacement therapy, ECMO, mechanical ventilation)							X				
Extubation and re-intubation date(s)						X					
Ordinal scale evaluation f	X				X	X	X	X	X	X	
Survival status					X					X	X
Quality of life (EQ-5D)											X
Glasgow Outcome Scale											X
Safety Assessments											
Safety laboratory tests g	X	X	X	X	X	X	X	X	X		
Creatinine h	X	X	X	X	X	X	X	X	X		
Vital signs i		X	X	X	X	X	X	X	X		
Adverse events j	X				X					X	X
Physical examination l	X	X	X	X	X	X	X				
Concomitant medications and procedures						X					
12-lead ECG	X							X			
PK/PD Assessments (Country-specific)k											
IFX-1 sample	X			X				X			

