## CONFIDENTIAL

Screening/ Randomization	Treatment Period IMP administration and assessments as long as in ICU / Hospital									Follow-up Period (Telephone possible)	
	Week 1			Week 2	Week 3	Week 4	Week 5	Any time			
	Screening not more than 24h before randomization	Day 1 (at-or up to 24h after random- ization)	Day 2	Day 4	Day 8	Day 15	Day 22	Day 28 (if still in hospital)	ICU discharge	Hospital discharge	Day 28
ADA sample	X										X
C5a sample	X				X						

ADA = anti-drug antibody; C5a = complement factor 5a; COVID-19 = Coronavirus Disease-19; ECG = electrocardiogram; ECMO = extracorporeal membrane oxygenation; EQ-5D = EuroQol 5-D; FUV = follow-up visit; ICU = intensive care unit; IMP = investigational medicinal product; IV = intravenous; PaO2 / FiO2 = oxygenation index; PK/PD = pharmacokinetic/pharmacodynamic; SARS-CoV-2 = Severe acute respiratory syndrome Coronavirus 2.

- a Obtaining of informed consent is proposed to be deferred or by any other legally acceptable local consent procedure for the ICU patients in this study (see Section 6.3).
- b Serum or urine samples for pregnancy testing will be collected only for women of childbearing potential.
- c PaO2 / FiO2 should be assessed within 6h before randomization (one representative measurement)
- d SARS-CoV-2 infection confirmation will be done, if not already tested positive in last 14 days before randomization, with locally available test system
- e Up to 6 treatments of IMP will be administered at days 1, 2, 4, 8, 15, and 22 as long as the patient is still in the hospital, even if discharged from the ICU.
- f 8-point ordinal scale score will be documented at the visits indicated, including the date (one value per assessment day, that best represents the patient's condition at that day)

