## 5.6.2. Phase III

### 5.6.2.1. End of Treatment and Follow-up

End of treatment (EOT) is defined as the last planned administration or discontinuation of IMP for other reasons.

The FUV is scheduled to occur 28 days (if patient has been discharged) and 60 days after the randomization date. The visit information obtained at a site visit or via telephone call (e.g., AEs, survival status, according to the SoA, Table 2) should be recorded.

Discontinuation of study treatment does not represent withdrawal from the study.

For details on treatment discontinuation criteria, see Section 7.2.4.

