#### 10.2.3.2. Secondary Efficacy Analyses

The secondary efficacy analyses will be performed based on the FAS.

The first secondary efficacy endpoint will only be addressed with statistical hypothesis tests if the primary endpoint is statistically significant using the full overall 2.5% one-sided alpha. If the first secondary endpoint is also statistically significant, the full 2.5% one-sided alpha will be passed to the 4 remaining secondary endpoints. Multiplicity in the secondary endpoints will be addressed with the fallback method. 60-day mortality will be analyzed similar to 28-day mortality and the other secondary endpoints will be evaluated using a logistic regression model with the explanatory variables randomized treatment arm (Arm B versus Arm A) and age for:

1. 60-day all-cause mortality
2. Proportion of patients with an improvement in the provided 8-point ordinal scale at day 15 (at least one score point lower than at randomization)
3. Proportion of patients with an improvement in the provided 8-point ordinal scale at day 28 (at least one score point lower than at randomization)
4. Proportion of patients developing acute kidney failure ( $eGFR < 15 \text{ mL/min}/1.73\text{m}^2$ ) during ICU stay and at day 28
5. Proportion of patients free of any renal replacement therapy within 28 days upon randomization
- 6.

The ordering of the secondary endpoints 2 to 5 for hypothesis testing will be as in above mentioned list. The full 2.5% one-sided alpha for the fallback method will be attributed to the 4 secondary endpoints in the following way 2%, 0.2%, 0.2%, and 0.1%. If the preceding hypothesis test is not significant, subsequent tests will be performed at the aforementioned alpha level. If tests are significant, the alpha is added to the subsequent hypothesis test (e.g., if the primary hypothesis test is significant and secondary endpoints 1-4 are all significant, the fifth secondary endpoint will be tested at an alpha of 2.5%; if the fourth secondary endpoint is not significant, the fifth secondary endpoint will be tested at an alpha of 0.1%).

The primary endpoint as well as all secondary endpoints will also be evaluated as censored time to event variables by Kaplan-Meier type methods. Kaplan-Meier analyses will be performed comparing the two treatment arms overall and within the following stratifications:

- Stratification by site
- Stratification by country

- Stratification by sex
- Stratification by age
- Stratification by comorbidities

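### Are the day-15 and day-28 ordinal-scale endpoints missing for patients who have already left hospital?

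*Combined protocol and SAP*

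**What the plan says.** Section 10.2.3.2 (version 4.0) puts two ordinal-scale endpoints in the tested secondary sequence: "Proportion of patients with an improvement in the provided 8-point ordinal scale at day 15 (at least one score point lower than at randomization") and "Proportion of patients with an improvement in the provided 8-point ordinal scale at day 28 (at least one score point lower than at randomization"). Both are analysed in the FAS by logistic regression on arm and age. They are reached only if 28-day and then 60-day mortality are significant. In the fallback step day 15 receives one-sided 2% and day 28 receives 0.2%. Section 4.2.2.3 adds an untested endpoint, a score of 3 or below on the same days.

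On collection, Section 8.2.2.2 states that the "8-point ordinal scale score will be documented at the visits specified in the SoA (Table 2"). The treatment-period heading of Table 2 reads "IMP administration and assessments as long as in ICU / Hospital", and its day-28 column is labelled "Day 28 (if still in hospital"). Footnote f says the "8-point ordinal scale score will be documented at the visits indicated, including the date". Section 5.6.2.1 places follow-up contacts at "28 days (if patient has been discharged) and 60 days after the randomization date", and Section 8.2.2.3 collects survival status at both.

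Section 10.2.3 leaves exact endpoint definitions and the handling of missing data to the SAP. No separate Phase III SAP is included in the combined document.

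**The concern.** The endpoints need a score on a fixed day, while the schedule collects scores only from patients still in hospital. The best states in Appendix 7 describe people who have left. Read literally, the score would be absent because the patient did well, and absent more often in the better arm. A logistic regression on recorded scores alone would lose its clearest successes. Day 15 carries most of the fallback alpha, so a biased or underpowered test there would also reduce what passes to day 28. A score taken at discharge belongs to another day and cannot show what happened afterwards.

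**Working it through.** **1. The plan's own figure.** The only stated power is 90% for mortality of 30% vs 15%. With n = 180 per arm, one-sided 2.5% and continuity correction:

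- null SE = √(0.225 × 0.775 × 2/180) = 0.0440
- alternative SE = √((0.21 + 0.1275)/180) = 0.0433
- power = Φ((0.15 − 1/180 − 1.96 × 0.0440)/0.0433) = 0.91

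The figure reproduces. The ordinal endpoints have no stated power, so no figure in the plan is in doubt.

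**2. Can the binary outcome be derived after discharge?** Section 6.2.1 requires invasive mechanical ventilation, so the baseline score is 6, or 7 with additional organ support (Appendix 7).

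- Improvement means 5 or lower from a baseline of 6, and 6 or lower from a baseline of 7.
- A patient at home scores 0 to 2, at least 4 points below baseline.
- To be misclassified as improved, a patient discharged home must, by the endpoint day, be dead, or be readmitted and back on invasive ventilation (with added organ support if the baseline was 7). Readmission on high-flow oxygen (score 5) is still an improvement.
- Deaths are known from survival status (Section 8.2.2.3). Re-intubation dates are to be recorded (Section 8.2.2.1).

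**3. Is the day-28 follow-up cell empty?** In the copy of Table 2 read here, rows have 11 cells for 12 visits, so one column is lost. Sections 8.2.2.4 and 8.2.2.5 place EQ-5D and the Glasgow Outcome Scale at day 60, and their only mark is in cell 11. Survival is marked in cells 10 and 11, and Section 8.2.2.3 names day 28 and day 60. On those anchors cell 10 is the day-28 follow-up contact, and the ordinal row is marked in cell 10. Counted from the left, cell 10 is hospital discharge instead. An empty day-28 follow-up cell is therefore not established.

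**4. How much does the handling rule matter?** The documents give no discharge rates, so these are assumptions: 15% of each arm improved while still in hospital, 180 per arm, one-sided 2% (the day-15 level). Counted as improved, the rate is 0.15 + d, where d is the discharged share. If discharged patients are dropped, it is 0.15/(1 − d).

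| Discharged, IFX-1 / placebo | Counted as improved | Power | Dropped | Power |
|---|---|---|---|---|
| 15% / 10% | 30.0% vs 25.0% | 0.16 | 17.6% vs 16.7% | 0.03 |
| 30% / 20% | 45.0% vs 35.0% | 0.45 | 21.4% vs 18.7% | 0.07 |
| 45% / 30% | 60.0% vs 45.0% | 0.79 | 27.3% vs 21.4% | 0.15 |

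Counted as not improved, the rates are 15% vs 15% throughout.

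**5. The level matters at day 28.** Assume, for placebo and IFX-1 respectively, 25% and 33% discharged, and 20% and 25% improved in hospital.

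- True improvement: 45% vs 58%. Unpooled SE = √((0.2475 + 0.2436)/180) = 0.0522, ratio 0.13/0.0522 = 2.49.
- Discharged dropped: 20/75 = 26.7% vs 25/67 = 37.3%, on 135 and about 121 patients.
- At 2.5%, power falls from 70% to 45%. Day 28 never receives 2.5%. It has 0.2%, or 2% + 0.2% = 2.2% if day 15 succeeds, where power is 35% vs 15% and 68% vs 43%.

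**The case for a change.** The strongest reply is that a confirmatory endpoint should not depend on an unwritten rule when the rule moves power this far. Four parts of it stand:

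- On any reading of Table 2 there is no contact on day 15 for a patient already discharged.
- No sentence in Section 10.2.3.2 says how such a patient is scored.
- Section 7.2.4 foresees transfer to another hospital, so leaving the study hospital need not mean going home.
- Sections 8.2.2.3 to 8.2.2.5 name the follow-up contact for survival, EQ-5D and the Glasgow Outcome Scale, while Section 8.2.2.2 does not name it for the ordinal scale. That is some evidence against a day-28 follow-up mark.

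Readmission is also not firmly covered elsewhere. Section 9.1 collects all adverse events to 30 days after the last dose, which for any dosed patient runs past day 28, but Section 9.1.1.1 reads more narrowly after discharge.

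The large losses in power, however, require a rule the plan does not contain. The complete-case illustration keeps deaths as failures, from survival status, while refusing to use discharge status for survivors. Dropping discharged patients would depart from the FAS, and scoring them as failures would contradict Appendix 7. Counting those discharged home and alive as improved, and the dead as score 8, agrees with both. What remains uncertain is the small group transferred, readmitted to ventilation or of unknown status. The untested endpoint of score 3 or below is somewhat more sensitive to readmission, since a readmitted patient on oxygen scores 4.

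**Conclusion.** The gap is real but is one of missing detail: the derivation for discharged patients is unwritten. Section 10.2.3 assigns that detail to the SAP, and an analyst would fill it in the one way consistent with the scale and the FAS. For patients discharged home alive the binary outcome is determined by the baseline score of 6 or 7. An extra score at the day-28 contact may already be scheduled and would alter very few outcomes. Both endpoints are tested only after two mortality tests succeed, so the primary conclusion is untouched.

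This rests on three assumptions: that the SAP, finalised before unblinding, does not adopt a complete-case rule; that ventilation again after discharge is uncommon among survivors; and that transfers are distinguished from discharges home. The power figures rest on assumed discharge rates and show only that the rule matters, not that the plan has chosen badly. The original Table 2 settles the day-28 follow-up cell; the conclusion does not depend on it.
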